We anticipate hiring PNCs with palliative care, cardiac, and/or psychiatric nursing experience and have commitments from three PNCs who have been providing this intervention during our pilot. These PNCs have received (or additional new PNCs will receive) training provided by study staff ([name]/[name]/[name]), which includes 28 hours of didactic and interactive role-play guided by an established training manual/protocol including specific intervention skills (e.g. problem solving, decision support, health coaching). [name]/[name]/[name] will review digitally-recorded mock training sessions and provide feedback until PNCs are confident in their skills. (See Nurse Coach Training scripts-Appendix C and Fidelity checklists - Appendix D).

Fidelity Monitoring: Treatment Integrity: PCT Consultation: Co-Is Drs. [name] and [name] will review PCT notes which are recorded in the electronic medical record using a template comprised of PCT elements based on NCP Guidelines.³⁶ If elements are consistently missing, the PCT member will receive additional training.

PNC coaching sessions: The PI and Drs. [name] and [name] will review a random sample of all digitally-recorded coaching sessions. The sessions will be scored using previously developed fidelity checklists that have been adapted to this study (see Fidelity Checklists-Appendix D.). The goal of the fidelity monitoring is to insure that the intervention is being administered reliably over time and across PNCs. PNCs who exhibit a pattern of non-adherence on three consecutive ratings will receive additional training and supervision.

Participant receipt / enactment of intervention: Following the collection of outcome measures at week 48, all intervention participants will be interviewed by phone for the primary purpose of determining if the patient received and enacted the components of the intervention as described in Table 2. We will use procedures and interview guides that have been adapted from our previous RCTs.⁶⁷ Briefly we will digitally-record, transcribe all interviews verbatim, and code transcripts using ATLAS.ti software to determine the extent of patient receipt and enactment of the skills taught by the nurse coaches. The PI is an experienced qualitative researcher,¹⁷⁰⁻¹⁷⁴ with expertise in the qualitative techniques that are recommended for intervention evaluation.^{175,176} Though not the purpose in this proposal, these interviews may also provide rich data for a secondary analysis of the patient and caregiver experience.

C4 INSTRUMENTS (All instruments are contained in Appendix E.)

The instruments were carefully chosen to measure distinct constructs within the theoretical models (Figures 1a and 1b) with little to no overlap. The proposed instrument battery and schedule are similar to what we have used in our prior studies^{50,51,177} and in our recent HF pilot study.⁶⁸ Per pilot participants' report⁶⁸ these presented minimal burden.

Table 3. Outcome measures

Specific Aim 1					
	Construct	Instrument	Description	Reliability	Schedule
HF Patients	QOL	Kansas City Cardiomyopathy Questionnaire (KCCQ) ¹⁷⁸	5 domains: physical limitations, symptoms, self-efficacy, social interference, and QOL; 23 items	Subscales α =.62 to .90	Baseline, week 8 and every 8 weeks until week 48
	Mood	Hospital Anxiety and Depression Scale (HADS) ¹⁷⁹	2 domains measuring depression and anxiety; 14 items	Subscales α =.82 to .83	
	Symptom Burden	Memorial Symptom Assessment Scale-HF (MSAS-HF) ²⁵	Targets 32 HF-relevant symptoms (e.g. chest pain, difficulty breathing while lying flat, etc.)	Subscales α =.73 to .92	
	Resource use	Resource Use	Inpatient days, ICU days, ED visits, hospice use, palliative care provider visits, AD completion, DNR orders	NA	
Specific Aim 2					
Caregivers*	QOL	Quality of Life – Caregiver (QOLC) ¹⁸⁰	3 domains: emotional and spiritual well-being; relationship with patient; & sleep, daily routine, and family life, 35 items	α = 0.91	Baseline, week 8 and every 8 weeks until week 48
	Mood	Hospital Anxiety and Depression Scale (HADS)	Same as above	Same as above	
	Caregiver burden	Montgomery Borgatta Caregiver Burden Scale (MBCB) ¹⁸¹	Measure of caregiver burden with 3 domains: objective burden, stress burden, and demand burden; 14 items	Subscales α = .75 to .88	
	Self-reported health	PROMIS SF Global Health ¹⁰	2 domains: physical and mental health, 10 items	Subscales α = .81 to .86	
Exploratory Aims					
HF Patients	Patient Activation	Patient Assessment of Chronic Illness Care (PACIC) ¹⁸²	5 dimensions: activation, delivery system/decision support, goal setting, problem solving, and coordination; 20 items	Subscales α =.62 to .90	Baseline, week 8 and every 8 weeks until week 48
	Coping style	Brief Cope	2 subscales: active and avoidant coping; 28 items ¹⁸³	α = .68 to .79	
	Social support	Multidimensional Scale of Perceived Social Support (MSPSS)	Perceived adequacy of support from family and friends, 12 items ¹⁸⁴	α =.81	
All	Health literacy	Newest Vital Sign ⁹	Measure of health literacy and numeracy based on interpretations of a nutrition label, 6 items	α = .76	Baseline only
	Demographics	Demographic questionnaire	Age, gender, race, marital status, religion, employment, education, occupation, health insurance, smoking, etc.	NA	

Additional measures and data

If patients die on study we will conduct a standardized interview with a study or non-study (if agreeable) caregiver 2 months after death using the instruments and similar techniques from prior studies^{129,185} to evaluate the caregivers' perception of the EOL care provided and to assess their grief experience and mood. The questionnaires are: 1) proxy-reported Quality of Death and Dying (QODD) (31-items) which rates the quality of the descendant's last 7 days; it has acceptable internal consistency (Cronbach alphas 0.89) and construct validity;^{186,187} 2) Inventory of Complicated Grief-Short form (ICG-SF) a reliable, validated 13-item survey of complicated grief¹⁸⁸ and the HADS (described above).

C4.1 Data Collection, Management, and Quality Control.

Participant recruitment/ tracking: A Microsoft Access database will be used to track the participant progress through recruitment, enrollment, and all study procedures. The database will consist of 3 sections: a form with contact information about interested participants (e.g., name, current address, cell and telephone numbers, and the best time to call); a section allowing for tracking contact attempts for potential participants; a dates form to document the number and outcomes of participant contacts (i.e., scheduled or enrolled), and all

subsequent contact times and types, specific mailed contacts, dates and times of pertinent communication, and information about the length of time between scheduled visits and dates of missed appointments.

Data collection of outcome measures: Several instruments are available for completion within the electronic health record. We are exploring the ability to collect most of the study data via this mechanism. In the event this is not feasible we will use our trained research coordinators to collect patient- and caregiver-reported data by phone and it will be directly-entered into our existing REDCap (Research Electronic Data Capture) database. REDCap is software for building and managing questionnaires and facilitating electronic data collection and storage. It supports a HIPAA best practice, secure web-based application enabling multiple sites to seamlessly access, analyze and share data while maintaining the security and integrity of the database and provides automated export procedures for seamless data downloads to common statistical packages (SPSS, SAS), built-in project calendars, scheduling and randomization modules. Hard stops prevent missing data due to inadvertent skipping of items.

eHR and administrative data collection: Resource use, advance directives, use of palliative, hospice, and home care services, disease stage, and other clinical data will be collected using established data collection forms and chart abstraction techniques/protocols that we have used previously.^{63,68,158} (See Appendix E for forms).

Data quality control (interviewing and chart abstraction): We will hire experienced research coordinators who have received intensive training (typically 10 hours including role play and inter-rater reliability checks) in order to assure high quality data collection from participants and electronic medical records.

Data Security: All databases are secure, HIPAA-compliant and password protected in both the front end and back end. Back end data will be housed on a secure drive with access limited to only authorized research personnel.

C5 STATISTICAL CONSIDERATIONS

C5.1 Randomization. After consent and baseline assessment, patients will be randomized using computer-generated treatment assignments, stratified by center (UAB or BVAMC), referring service (HF clinic, cardiology, primary care), and race (Caucasian/non-Caucasian).

C5.2 Statistical Analyses

Specific Aim 1 Patient-reported QOL, mood, symptom burden, and resource use

The intention to treat (ITT) analysis will be used for all treatment comparisons. That is, all randomized patients will be included in primary comparisons, regardless of whether the patient actually received the randomly-assigned intervention. Primary data analysis will begin with descriptive statistics for baseline patient characteristics and outcomes by treatment group. Distributional assumptions will be examined; when appropriate we will employ testing and modeling procedures that do not assume normality. We will compare groups with respect to baseline covariates. We will analyze and compare missing data and compliance patterns according to baseline covariates and we will adjust analyses for baseline factors showing either imbalances or predictive of missing data (not due to patient death) or compliance. Mixed modeling techniques and covariate adjustment will reduce the impact of missing data, provided that the data are missing at random. If necessary, multiple imputation techniques and sensitivity analyses will be used to deal with data not missing at random and not caused by patient death.

We will conduct 2 sets of longitudinal ITT analyses of the primary study endpoints for participants with baseline and one or more follow up assessments using mixed effects modeling for repeated measures to examine the relative impact of ENABLE: CHF-PC in the 48 weeks after enrollment (forward in time from baseline), and its effects proximal to the time to death (retrospective starting from death). In the first set of analyses, we will examine differences between all patients in each group surviving until the scheduled 48 week follow-up surveys. Kurland et al.¹⁴⁷ have described this approach as a partially conditional analysis for joint longitudinal and survival data, because it assumes that patients are alive at the comparison times.¹⁴⁷ Initial ITT analyses will be conducted on patient-reported outcomes using mixed effects models to test the effect of the intervention, first by comparing all group differences simultaneously for both time periods in multiple degree of freedom global tests, and then individually if overall differences are significant.

The second analysis, retrospective from death, also conducted with mixed effects models, has been described by Kurland et al.¹⁴⁷ as fully conditional; because it examines patient outcomes conditional on the patients having died (the participants who are alive by the end of follow-up are excluded because their outcome measures proximal to death will be unknown). Alternative more complex analyses involving “terminal decline” models that jointly model a longitudinal outcome and survival will be considered as described under Exploratory Aim 2 below. All calculations will be performed using the latest versions of SAS and R. Standardized intervention effect sizes will be estimated for each outcome, and the False Discovery Rate criterion will be used to correct for multiple significance testing. We will conduct a decedent-only ITT analysis for the proxy-report QODD. Since only one QODD observation will be available for each decedent, no longitudinal modeling is required. Secondary analyses will consider any deviations from the intended intervention, and intervention dose effects. Subgroup analyses will be conducted with interest on

determining the profile characteristics (e.g. race, SES, gender, military vs. civilian background, absence of caregiver, etc.) of the participants who benefited the most and the least from the intervention using flexible modeling techniques, such as latent class analysis and recursive partitioning.

Specific Aim 2 Caregiver QOL, mood, self-reported health, burden

Caregiver outcomes will be analyzed using the same longitudinal methods as outlined for Specific Aim 1. For the analyses going forward in time from baseline, the effects of patient death on caregiver outcomes will be examined using models with indicators for patient death at its respective time-point. Only decedents' caregivers will have grief outcomes analyzed which will not involve longitudinal modeling. Caregivers of patients who die will contribute the additional outcome of a rating of quality of care at the end of life (QODD). Since only one QODD observation will be available for each decedent, no longitudinal modeling is required. However, analysis of these measures will be conducted with mixed effect methods to account for nesting, with the parameter of interest being the association between group assignment and the caregiver-rated outcome

Exploratory Aim 1. Explore mediators/moderators of patient/caregiver outcomes and reciprocal relationships.

As depicted earlier in Figure 1a, intervention effect on patient QOL, mood, and symptom burden is proposed to be mediated by the quality of chronic illness care (PACIC), active and avoidant coping styles (COPE), social support (MSPSS) and health literacy (NVS). This conceptual logic will be tested using structural equation modeling (SEM) applied to matrices residualized for demographic and disease factors.¹⁸⁹ Each patient model will involve 13 observed variables: the intervention as a dichotomous variable, five mediational variables (8 week: PACIC, active COPE, avoidant COPE, MSPSS, NVS) lagged against their five baseline values, and the 8 week outcome of interest lagged against its baseline. With 22 degrees of freedom, a sample size of 359 (expected to be alive/available at week 8), and a significance level of $p = .05$, power is .86 to distinguish a model with close fit (root mean square error of approximation [RMSEA] = .05) from a model with mediocre to poor fit (RMSEA = .09).¹⁹⁰ Jointly significant effects involving the theorized mediators (intervention → mediator, mediator → outcome as depicted in Figure 1a) will constitute evidence of mediation. Assuming a medium effect size ($d=0.5$) on mediator and outcome, a sample size of 359 provides .80 power to detect a small indirect effect of at least 34% of the total intervention effect size ($d_M=0.17$) based on computer simulations of joint tests with a significance level of 0.05.¹⁹¹

As depicted earlier in Figure 1b, the effect of the intervention on caregiver QOL, mood, and burden is proposed to be mediated by patient well-being. Tests of mediation of caregiver outcomes will involve jointly significant ($p = .05$) effects (intervention → 8 week patient outcome → 24 week caregiver outcome) for caregiver outcomes mediated by patient outcome. Assuming a medium effect size ($d=0.5$) on both mediator and outcome, a sample size of 188 (expected CGs with 24 week outcomes) provides .80 power to detect an indirect effect size of at least 48% of the total intervention effect size ($d_M=0.24$) based on computer simulations of joint tests with a significance level of 0.05.¹⁹¹ As depicted earlier in Figure 1b, the effect of the intervention on caregiver QOL, mood, and burden is proposed to be mediated by patient well-being. Tests of mediation of caregiver outcomes will involve jointly significant ($p = .05$) effects (intervention → 8 week patient outcome → 24 week caregiver outcome) for caregiver outcomes mediated by patient outcome. Assuming a medium effect size ($d=0.5$) on both mediator and outcome, a sample size of 188 (expected CGs with 24 week outcomes) provides .80 power to detect an indirect effect size of at least 48% of the total intervention effect size ($d_M=0.24$) based on computer simulations of joint tests with a significance level of 0.05.¹⁹¹

Exploratory Aim 2. Examine intervention effects using joint modeling approaches.

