The next phase of this research (including Drs. [name]/[name]-co-Is; proposal under review, HSRD) is a national, 48-AMC site implementation project. The team has also pursued several studies of a hospice emergency kit (HEK) developed by [name] and implemented as a BVAMC standard of care for veterans being discharged to home hospice. The most recent published study was a prospective cohort of 45 patient/caregiver dyads (12% with HF) in home hospice (enrolled in less than 9 months)¹⁶⁶ provided promising evidence that HEKs are a feasible, well-tolerated method for achieving timely relief of emergent symptoms and possibly avoiding unwanted ED visits and hospitalizations. Finally, the BVAMC participated in a multi-site RCT of discontinuation of statins in home hospice patients conducted by the NINR-funded *Palliative Care Research Consortium* ([name]/[name]-site-PIs). The BVAMC was one of the top recruiters, demonstrating our ability to screen and enroll eligible palliative care patients for clinical trials.

Relevance to the proposed study: Demonstrates successful collaboration among the proposed study investigators and expertise in conducting multi-site palliative care intervention studies within and outside the VA system.

Summary of Preliminary Work: ENABLE, one of the first community-based concurrent palliative care models to demonstrate effectiveness in reducing the burden of serious illness for patients and caregivers, has undergone more than a decade of systematic intervention development and effectiveness research in cancer and formative evaluation in advanced HF. The UAB/BVAMC teams have conducted important HF/palliative care studies using population-based methods, demonstrated the ability to recruit and deliver interventions to minority HF populations, and to conduct multi-site palliative care research. We are poised to undertake a full scale pragmatic RCT in underserved HF patients and caregivers.

C2 STUDY DESIGN

The figure illustrates the study schema for this prospective pragmatic RCT of ENABLE CHF-PC, a theoretically-based early palliative care model that is integrated with advanced HF care compared to usual care. Our goal is to determine intervention effects on patient QOL, symptom burden, anxiety, depression and resource use (primary) outcomes and caregiver QOL,

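### Resource use is a primary outcome with no analysis of its own, and neither stated analysis of the primary endpoints compares all randomised patients on use up to death

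*Combined protocol and SAP*

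**What the plan says.** - **Status.** C2 (Study Design) closes its list of patient outcomes with "depression and resource use (primary) outcomes". The Specific Aim 1 heading in C5.2 repeats it: "Patient-reported QOL, mood, symptom burden, and resource use".
- **Content.** Table 3 (C4) defines resource use as "Inpatient days, ICU days, ED visits, hospice use, palliative care provider visits, AD completion, DNR orders". These are counts of days and visits, together with items that either occur or do not.
- **Source.** C4.1 says that resource use and related clinical data "will be collected using established data collection forms and chart abstraction techniques/protocols". It is not a questionnaire score.
- **Analysis.** C5.2, Specific Aim 1, states: "We will conduct 2 sets of longitudinal ITT analyses of the primary study endpoints for participants with baseline and one or more follow up assessments". For the first set, "we will examine differences between all patients in each group surviving until the scheduled 48 week follow-up surveys"; the text then labels this a partially conditional analysis that takes patients to be living when they are compared. The second set works backwards from death and leaves out everyone alive at the end of follow-up.
- **Population.** The same section opens with an intention-to-treat statement under which every randomised patient enters the primary comparisons.
- **Elsewhere.** The initial mixed-model tests in C5.2 are described for patient-reported outcomes. The joint model with survival is under Exploratory Aim 2, and its combined estimate is stated for quality of life. Table 4 gives detectable differences for KCCQ, MSAS-HF and the two HADS scales, with no column for resource use.

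**The concern.** Conditioning on being alive is a recognised choice for a questionnaire score, because a dead patient has no score. Resource use is different: a patient who dies has used some amount of care up to that day, and the charts can show it without a survey. The background (A7) cites less aggressive treatment at the end of life and longer hospice stay among the expected results of better communication and planning, so the weeks before death matter for this outcome.

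Two things are at stake. First, both stated sets compare groups formed by survival after randomisation. If the intervention changes survival, which Exploratory Aim 2 treats as worth evaluating, the arms in each set are no longer the randomised arms. Second, inpatient days, ICU days and ED visits accumulate with time alive. Without an exposure term or a rule for death, lower use and shorter life cannot be told apart. Since no method is written for this outcome, the choice would be made after the data are seen.

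**Working it through.** **Inputs.** 380 patients, 190 per arm (C2.3). Exponential survival with a median of 2 years, and independent attrition of 10% over 2 years (C5.3). Surveys every 8 weeks to week 48 (C3.1). Two years is taken as 104 weeks.

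**1. Reproduce Table 4.** Alive and available at week w = 380 × 0.5^(w/104) × 0.9^(w/104).

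| Week | Computed | Table 4 |
|---|---|---|
| 8 | 357.4 | 356 |
| 16 | 336.1 | 334 |
| 24 | 316.0 | 313 |
| 32 | 297.2 | 294 |
| 40 | 279.5 | 276 |
| 48 | 262.9 | 259 |

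All are within 3%, so the survival and attrition assumptions are read as the plan intends.

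**2. Deaths by week 48.** 380 × (1 − 0.5^(48/104)) = 380 × (1 − 0.7262) = 104. Taking two years as 96 weeks gives 111. C5.3 states 120. That figure is close to 380 − 259 = 121, which also counts patients lost to attrition.

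**3. Deaths before the first follow-up.** 380 × (1 − 0.5^(8/104)) = 380 × (1 − 0.9481) = 19.7, about 20. These patients have no follow-up assessment, so on the stated rule they enter neither set.

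**4. Who enters which comparison.**

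| Patients | Forward set | Backward set |
|---|---|---|
| Die before week 8 (about 20) | no | no |
| Die between weeks 8 and 48 (104 − 20 = about 84) | at most up to the last assessment before death | yes, if assessed |
| Alive at week 48 (380 − 104 = about 276) | yes, if assessed | no |

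No column holds all 380 patients with their use up to death. For those who die after week 8, the forward set has two readings. Taken literally, "surviving until the scheduled 48 week follow-up surveys" removes them altogether. Taken with the partially conditional label, they contribute their earlier assessments.

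**5. Share of use omitted.** This needs the ratio of use near death to use at other times, and whether abstraction stops at the last survey. The documents give neither, so no percentage is offered.

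**The case against.** The strongest reply is that the plan is silent on resource use rather than wrong. The initial mixed-model tests are written for patient-reported outcomes, the follow-up-assessment rule is not defined for chart data, and the intention-to-treat statement already promises all randomised patients. An analyst could therefore include everyone. This is fair as far as it goes. But C5.2 applies its two restricted sets to the primary study endpoints, of which resource use is one, and offers no other analysis. The promise and the restriction cannot both hold.

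A reader might infer several stronger things that the documents do not support:

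- *That the analysis of survivors is the only primary analysis, so use near death is never examined.* The backward set could capture it, though in decedents only, which is not a randomised comparison.
- *That counts will be forced into a normal model.* C5.2 allows procedures without a normality assumption where appropriate. What is missing is a named count model, an exposure term and a rule for death.
- *That chart data exist for every patient to death or week 48.* The Usual Care text places some primary care in patients' local communities, C2.3 expects 10% withdrawal or loss, and nothing says that abstraction continues after withdrawal.
- *That dividing by time alive removes the effect of survival.* It does not. Suppose, purely for illustration, one unit of use per week, rising to five in the last four weeks of life. A death at week 20 gives (16 + 20)/20 = 1.8 units per week; a death at week 40 gives (36 + 20)/40 = 1.4, with the same pattern of care.

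**Conclusion.** The concern holds as a gap in specification combined with a conflict inside C5.2. A primary outcome has no analysis of its own. Of the two sets stated for the primary endpoints, one conditions on survival and the other drops survivors, so neither delivers the all-randomised comparison that the section promises. The exploratory joint model does not fill the gap, because its combined estimate is stated for quality of life.

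By size, about 104 (recomputed) to 120 (stated) of 380 patients die within 48 weeks, and about 20 would enter neither set. These counts rest on the plan's exponential survival with a 2-year median. The 20 also rests on reading the follow-up-assessment rule as applying to resource use. The effect on the arm contrast cannot be quantified from the documents. It should be corrected before analysis, though it does not bear on the patient-reported outcomes.

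**What to change.** 1. In C5.2, exempt resource use from the follow-up-assessment and alive-at-survey restrictions, and reconcile the intention-to-treat statement with the populations of the two sets.
2. Make the primary resource-use comparison one over all randomised patients, from randomisation to death, end of chart observation or week 48, whichever comes first. State whether abstraction continues after withdrawal from surveys.
3. For inpatient days, ICU days and ED visits, use a count model (for example negative binomial) with log(days observed alive) as offset and the C5.1 stratification factors (centre, referring service, race) as covariates.
4. For hospice use, and for advance directives and DNR orders not already in place at baseline, compare cumulative incidence with death as a competing event.
5. Report palliative care provider visits with the consultation that the intervention itself supplies (C3) shown separately.
6. Present all of these beside the survival comparison, since a rate per day alive does not fully separate use from survival. A joint or composite estimand would be a defensible alternative if stated in advance.

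The cost is SAP text and modest programming, with no new visits or instruments. The downsides are that resource use is analysed differently from the patient-reported outcomes, and that use outside the two centres' records may be incomplete and should be reported as a limitation.

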Patients ≥ 65 years will be recruited from the UAB and BVAMC cardiology, advanced HF, geriatric, and primary care clinics and from [name] (co-I)^{160,163} existing UAB HF study cohorts. HF occurs most commonly in older adults and the Seattle Heart Failure model¹⁶⁷ has demonstrated some ability to identify patients who might benefit from palliative care.⁴¹ These broad criteria, consistent with a pragmatic design, balance the competing issues of sample homogeneity and external validity/generalizability.

Patient Inclusion Criteria: 1) English-speaking; 2) able to complete baseline interview (see Instruments-Appendix E); 3) Age ≥ 65 ; 4) NYHF III/IV or ACC Class D HF (physician-determined); 5) Seattle Heart Failure Model $\geq 50\%$ 2 year mortality (<http://depts.washington.edu/shfm/>)^{41,167}

Patient Exclusion Criteria: 1) Dementia or significant confusion (measured by ≤ 3 Callahan score¹⁶⁸ 2) DSM-IV Axis I diagnosis (e.g. schizophrenia, bipolar disorder, or active substance use disorder); 3) Patients will not be excluded if they do not identify a caregiver.*

* We have consciously chosen to make allowances (in this and our prior intervention studies) in favor of a pragmatic approach recognizing that many chronically-ill patients have little or no caregiver support. We recognize that caregiver support can positively influence some HF outcomes and if imbalance.^{39,110,169}

Specific Aim 2 Caregiver Sample and Justification

Consistent with our prior studies^{50,51,63 102} and a pragmatic design we will use a broad definition of "caregiver".

Caregiver Inclusion Criteria: 1) Identified by the patient as "a person who knows you well & is involved in your medical care". May live in the same household and/or be considered to be primary caregiver willing to participate;¹⁰² 2) English-speaking; 3) able to complete baseline interview (see Instruments-Appendix E)

C2.3 Total Enrollment

We anticipate a total enrollment of 380 patient participants and 228 caregivers over 42 months (from our previous studies, ~60% caregivers participated). Approximately half of the patient participants (n=190) will be randomized to the intervention and half (n=190) will be randomized to receive usual HF care. Likewise, due to stratified randomization by indication of caregiver, approximately half of caregivers (n=114) will be randomly assigned to intervention and the other half to usual care (control) (n=114).

Justification of Enrollment Estimates

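### C2.3 says randomisation is stratified by indication of caregiver, C5.1 does not list that factor: reconcile the two, and pre-specify the randomisation factors in the models

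*Combined protocol and SAP*

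**What the plan says.** Section C2.3 (Total Enrollment) sets the size of both samples: "We anticipate a total enrollment of 380 patient participants and 228 caregivers over 42 months (from our previous studies, ~60% caregivers participated"). Patients are allocated 1:1: "Approximately half of the patient participants (n=190) will be randomized to the intervention and half (n=190) will be randomized to receive usual HF care". For caregivers the section gives a reason for the even split: "due to stratified randomization by indication of caregiver, approximately half of caregivers (n=114) will be randomly assigned to intervention", with the other 114 in usual care.

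Section C5.1 (Randomization) describes the allocation itself: "After consent and baseline assessment, patients will be randomized using computer-generated treatment assignments", and these are "stratified by center (UAB or BVAMC), referring service (HF clinic, cardiology, primary care), and race (Caucasian/non-Caucasian"). Caregiver status is not in that list, and no other section adds it.

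Three further places bear on the point:

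- The criteria in C2.2 make caregiver status vary between patients ("Patients will not be excluded if they do not identify a caregiver"), and the footnote there acknowledges that "caregiver support can positively influence some HF outcomes".
- Section C5.2 (Statistical Analyses) gives the covariate rule: "we will adjust analyses for baseline factors showing either imbalances or predictive of missing data", or predictive of compliance. It does not name the stratification factors or caregiver status. Absence of a caregiver appears later in C5.2 only as one characteristic for subgroup exploration.
- Section C3.1 (General Study Procedures) orders the steps as screening, consent, baseline data collection and randomisation, followed by coach contact with intervention patients and any enrolled caregivers.

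**The concern.** The two sections describe different allocation schemes. A programmer building the list from C5.1 would leave out the factor on which C2.3 relies, and one reading C2.3 would add it. The strata to program, report and carry into the analysis are therefore not settled.

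Two things are at stake. The first is balance. The plan recognises caregiver support as an influence on patient outcomes, and about 40% of patients are expected to have no participating caregiver, so chance differences between arms are possible if caregiver status is not a stratum. The second is the analysis. When randomisation is stratified, a model that contains the stratification factors gives standard errors that match the design. C5.2 instead waits to see which baseline factors are imbalanced, or predict missingness or compliance. That leaves the primary model undetermined until the data are seen and may omit the very factors used to randomise.

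**Working it through.** **Inputs.** 380 patients, 190 per arm, about 60% with a caregiver (C2.3). Two-sided alpha 0.01, power 0.80, intra-subject correlation 0.5 (C5.3). Caregivers available per arm: 107, 101, 94, 88, 83 and 78 at weeks 8 to 48 (Table 5, where this column is half of each total).

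**The plan's own figures.** 380 × 0.60 = 228, and 228 / 2 = 114 per arm, as stated. Table 5 also reproduces on equal arms. The standardised detectable difference is

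(z₀.₉₉₅ + z₀.₈₀) × √[(1/n₁ + 1/n₂)(1 + (m − 1)ρ)/m],

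where m counts baseline plus the follow-ups so far. At week 8 (n = 107, m = 2) this gives 0.405. At week 48 (n = 78, m = 7) it gives 0.414. The four times between give 0.393, 0.394, 0.399 and 0.405, all as printed.

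**Caregiver split without a caregiver stratum.** With 228 of 380 patients having a caregiver and 190 patients drawn into one arm, the number of caregivers in that arm is hypergeometric:

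- Mean 190 × 0.6 = 114.
- SD = √(190 × 0.6 × 0.4 × 190/379) = 4.78.
- 95% range 114 ± 1.96 × 4.78 = 104.6 to 123.4, that is 105 to 123.
- Probability of exactly 114/114: 0.08. Of being 5 or more away from 114: 0.35. Of being 10 or more away: 0.05.

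A looser bound, Binomial(228, 0.5), has SD 7.5 and range 99 to 129.

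**Effect on the caregiver comparison.** At a 123/105 split the standard error grows by √[(1/123 + 1/105)/(2/114)] = 1.003.

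| Split | Power | Week-48 standardised MDD |
|---|---|---|
| 114/114 | 0.800 | 0.414 |
| 123/105 | 0.797 | 0.415 |
| 129/99 (binomial bound) | 0.792 | 0.417 |

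**Effect on the patient comparison.** The between-arm difference in the proportion with a caregiver has a 95% range of ±2 × 1.96 × 4.78/190 = ±0.099, about 10 percentage points. An unadjusted arm difference then shifts by at most about 0.099 times the outcome difference between patients with and without a caregiver. The documents do not give that difference. As an assumed range for KCCQ, take it as anything from the week-48 MDD (6.72) to a full SD (21): the shift at the edge of the range is 0.099 × 6.72 = 0.7 to 0.099 × 21 = 2.1 points.

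**Number of strata.** C5.1 gives 2 × 3 × 2 = 12 cells, and a caregiver factor makes 24. C2.3 expects 240 of roughly 4,900 eligible patients from BVAMC. If enrolment is proportional (an assumption), that is about 19 of 380 patients, or about 19/12 = 1.6 per BVAMC cell with 24 cells, against 19/6 = 3.2 with 12.

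**The case against.** The strongest reply is that little depends on the conflict. C2.3 claims only approximate halves, which 1:1 patient randomisation delivers in expectation. A reader might infer that the 114/114 caregiver sample is wrong or that Aim 2 loses power; the figures above do not support that.

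A reader might also infer that C5.1 is the scheme that will be run. It is the randomisation section, so this is plausible, but no text sets precedence, and the factor may simply have been left off the C5.1 list.

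A third tempting reading is that caregivers can join after allocation. The documents do not say so: C5.1 and C3.1 place consent and baseline before randomisation, and C2.2 requires a caregiver to be able to complete the baseline interview. What remains is that neither section states the timing for caregivers explicitly.

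Nor would the C2.3 stratum by itself fix the Aim 2 population. Its factor is the patient indicating a caregiver, and a named caregiver may still decline or be ineligible.

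Finally, the footnote in C2.2 concerns caregiver support in general and breaks off where the handling of imbalance would follow, so it is limited evidence of prognostic strength. The imbalance rule in C5.2 could also catch caregiver status. That is true, but a rule triggered by the observed data is not a commitment, and it does not say which strata were used.

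**Conclusion.** The conflict between C2.3 and C5.1 stands and must be reconciled; which section governs is unknown. Its numerical effect on the caregiver arms is negligible, a power loss of about 0.3 points at the edge of the 95% range, so the caregiver sample size does not need to change. The range assumes exact 190/190 arms and 228 caregivers, and ignores any association of caregiver status with the C5.1 strata. The binomial bound still costs under one point.

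The substantive loss is guaranteed balance on a factor that the plan regards as able to influence outcomes, together with a covariate rule that does not commit to the randomisation factors. The shift from a chance imbalance is probably small, but its size depends on a caregiver effect that the documents do not give. The reason to act is that a core design element is stated in two ways and the correction is nearly free.

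**What to change.** 1. Choose one scheme and make both sections say it. Either add caregiver indicated by the patient (yes/no), recorded before allocation, to the C5.1 strata, or delete the stratification phrase from C2.3 and leave the expected split as a consequence of 1:1 allocation.
2. Under either choice, pre-specify centre, referring service, race and baseline caregiver status as covariates in the patient mixed models. In the caregiver models, where caregiver status is constant, pre-specify centre, referring service and race. The C5.2 rule on missingness and compliance can remain as an addition.
3. State in C3.1 or C5.1 that caregiver consent and baseline assessment are completed before the patient is allocated, in both arms.

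The covariates cost five degrees of freedom in the patient models (1 + 2 + 1 + 1) and four in the caregiver models. Adding the stratum doubles the cells to 24 and leaves the BVAMC cells sparse, so minimisation or small blocks would be needed; the documents give no block size. Deleting the phrase avoids that cost and leaves caregiver status to be handled by adjustment.
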